10.1.4 Reporting and Follow-up

The investigators shall record all AEs that occur during the study, including the name, start and end

dates, severity, causality relationship with the device, and outcome of each AE, as well as any action taken for each AE.

The investigators shall provide symptomatic treatment and follow-up for each AE until all symptoms disappear or become stable, or otherwise there is another reasonable explanation.

10.2 Serious Adverse Event

10.2.1 Definition

A Serious Adverse Event (SAE) refers to any AE occurrence during a clinical study that causes any of the following situations:

- death; or
- serious deterioration in the health of the patient, including:
 - a life-threatening illness or injury; or
 - a permanent impairment of a body structure or a body function; or
 - involved or prolonged inpatient hospitalization;
 - medical or surgical intervention to prevent permanent impairment to a body structure or a body function;
- fetal distress, fetal death or congenital abnormality or birth defect.
- Other medically significant events.

All definition above comes from *Good Clinical Practice for Medical Devices*.

Note: Planned hospitalization for a pre-existing condition or a procedure required by the clinical investigation plan, without serious deterioration in health is not considered an SAE.

10.2.2 Reporting of SAEs

For SAEs, investigators shall conduct a comprehensive analysis and assessment of the SAE immediately after becoming aware of it, including its severity and relationship to the observational device. For suspected SAE related with medical device, investigators shall report to relevant personnel. For SAEs lead to death or SAEs lead to serious injury, reports must be submitted within reported within the prescribed time frame.

11 Clinical Event Committee

The Independent Clinical Event Committee (CEC) will evaluate safety endpoints data and the sponsor will appoint a CEC composed of physicians (not investigators) to rule uniformly adjudicate all SAE and/or AEs associated with the observational device or observational procedure identified. Only CEC's determinations of the collected data (Data collection includes patient medical records, laboratory tests, and, if necessary, patients' imaging data) were used for the analysis of safety endpoints.

12 Protocol Amendments

If there is any modification to the protocol after EC approval, a "protocol revision statement" or revised protocol is required, which shall be signed and confirmed by the sponsor and the coordinating investigator and approved by the EC before implementation.

13 Direct Access to Source Data and Documentation

Source data refers to the original records of clinical findings, observations, and other activities in a medical device clinical study, as well as all information in certified copies, which can be used for the reconstruction and evaluation of the clinical study.

Source documents refer to printed documents, visual files, or electronic files that contain source data.

The archived materials for this clinical study include: (1) clinical study protocol; (2) electronic case report forms (eCRFs); (3) informed consent forms (If any); (4) original medical records of the patients; (5) statistical analysis reports; (6) all other materials such as interim reports and final summary reports of the clinical study.

Investigators must carefully complete all study documents, including the confirmation of all participated patients (effectively verifying different records, such as eCRFs and original hospital records), all original signed informed consent forms of patients (if any), and detailed records in all eCRFs. After the study is completed, all clinical study documents shall be submitted to the clinical research institution for safekeeping.

14 Clinical Study Report

The contents of a clinical study report for a medical device clinical study shall include its general information, conduct, statistical analysis methods, study results, reports of AEs and their handling, analysis and discussion of study results, clinical study conclusions, ethical description, finding, and suggestions for improvement.

15 Principle of Confidentiality

The protocol is confidential, which is provided to related medical experts, related personnel such as investigators participating in the study, and authorized agencies for related operations such as medical institutions undertaking this study, ECs and Contract Research Organization (CRO). Besides explaining situation to patients, any content of this protocol shall not become public or be disclosed to a third party without a prior written agreement from the sponsor. In addition, if any part of or all results of this clinical study are going to be published in external media such as societies and journals, written approval from the sponsor shall be obtained.

The contents of this clinical study and all the attached materials are confidential, exclusive to the sponsor, and investigators shall be responsible for the confidentiality. No confidential information, including patent application, manufacture process and unpublished data that the sponsor provides investigators, shall be disclosed to any third party unless being agreed by the sponsor, and the confidentiality obligation remains valid after termination or end of this study.

Investigators and their staff will collect patients' personal data being used in this study ("study data"), including date of birth, gender, identity card, home address, photos and physical or mental health data.

All medical records and research materials that can identify patients will be kept confidential within the scope of law. However, the management departments of clinical research institutions, ECs, drug regulatory authorities, healthcare administrative departments or monitors, auditors are allowed to review the personal data of patients participating in the clinical study as necessary to perform their work in accordance with the prescribed procedures. All personal information in the study will be handled in accordance with the national and local data protection laws.

Patients have the right to request investigators and sponsor to protect their information and to correct any inaccurate information in such data. If patients withdraw informed consent, investigators will no longer use or disclose their data, and sponsor may still use the data acquired before withdrawing.

The study results may be published in medical journals and presented at medical conferences. Patients will not be identified in any of these publications.

16 Responsibilities of All Parties

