Endpoint	
Safety Endpoints[Adjudicated by Clinical Event Committee (CEC)]
 
1) stroke Rate2) All-cause Mortality3) Lesion-Related Symptoms or Signs Rate4) Lesion-Related Complication Rate (Immediate post-procedure)5) Adverse Event (AE), Serious Adverse Event (SAE)
Statistical Analysis Method	
Efficacy Endpoints
 
1) Imaging Evaluation of Target Aneurysm [O'Kelly-Marotta(OKM) Grade]2) Adequate Occlusion Rate of Target Aneurysm (Base Raymond-Roy Grade)3) Technical Success rate (Immediate post-procedure)4) Re-sheathing Performance (Immediate post-procedure)5) Modified Rankin Scale (mRS) Change from Baseline 
Sample Size Estimation This study is an observational study that does not involve statistical hypotheses. Therefore, the plan is to collect data on as many patients as possible who received FRED treatment for intracranial aneurysms in China from May 2023 to May 2027, and as such, there is no specific sample size estimation.
 
Statistical Analysis Datasets The dataset will consist of all study patients who meet the inclusion and exclusion criteria.
 
General Principles of Statistical Analysis Detailed information on statistical analyses will be described in a separate Statistical Analysis Plan (SAP), with the final version of the SAP to be completed prior to database lock. The statistical analysis will be performed for this study using SAS® (version 9.4 or

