4.4 Endpoint

4.4.1 Safety Endpoint

(1) Stroke Rate

Definition: The stroke rate refers to the proportion of stroke patients in the total number of patients.

Collection Content: Record the date of stroke, type (ischemic or hemorrhagic), severity (mild, moderate, severe), location and cause, treatments, or other interventions for stroke, and whether the

stroke resulted in the patient's death. Also assess the relationship of the stroke event to the observational device and the patient's concurrent antithrombotic therapy. All stroke events are assessed by the CEC.

(2) All-cause Mortality

Definition: Mortality refers to the proportion of dead patients in the total number of patients.

Collection Content: Record the date of the death event and whether it was neurogenic. Evaluate the relationship of the death event to the observational device. Neurogenic death is defined as a death event directly resulted from a neurologic cause judged by the Clinical Event Committee (CEC).

(3) Lesion-Related Symptoms or Signs Rate

Definition: Lesion-related symptoms or signs rate refers to the proportion of patients with lesion-related symptoms or signs to total patients.

Collection Content: All neurological related symptoms which were not present at baseline or worsened from baseline will be record including headache, hemiplegic paralysis, seizure, aphasia, stroke, bleeding (including intracerebral, subarachnoid hemorrhage, retroperitoneal, others), facial nerve pain, seizures, vision loss, aphasia, hemiplegia, oculomotor nerve palsy, neck pain or stiffness, loss of consciousness, meningeal irritation, pre-retinal hemorrhage, increased intracranial pressure, other aneurysm-related symptoms, or abnormal signs (list specific symptoms or abnormal signs).

(4) Lesion-Related Complication Rate

Definition: Lesion-related complication refers to the proportion of patients with lesion-related complication to total patients.

Collection Content: Record whether the following complications occurred during the procedure. Principal Investigator (PI) shall evaluate the relationship between complications and observational device, other interventional devices, and surgical procedures.

- Complications of arterial puncture: including puncture site pain, puncture site local bleeding, injury to the puncture artery or adjacent nerves,;
- Dissection or perforation of the parent artery,
- Rupture or perforation of the aneurysm,
- Vasospasm;
- Stent thrombosis,
- Other complication

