(5) Adverse Event, Serious Adverse Event (AE, SAE)

Definition: Refer to section 10 in this protocol.

Evaluation method: All Adverse Events (AEs) observed or reported will be assessed and recorded, and the causality and severity of AEs will be assessed according to the definitions and causality

assessment in Section 11 of this protocol.

The Principal Investigator (PI) shall assess whether an AE/ SAE meet the definition of surgical complication and safety collection index. If yes, the investigator shall complete corresponding surgical complication or safety evaluation indicator page.

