Identification of Confounding Variables: Potential confounders will be systematically identified. Any variable suspected to be a confounding factor, based on existing evidence, will be carefully documented. Factors that may influence both the intervention and the outcome will be thoroughly considered, and data collection will be as comprehensive as possible to ensure robust adjustment for confounding in the final analysis.

Clinical Events Committee: Medical data requested in the protocol will be provided to Clinical Events Committee under patient information protection for review. The personnel requirements of the CEC member and the contact details of the corresponding personnel will be recorded in a separate file. Evaluation and adjudication of safety endpoints as specified in the protocol will be completed by an independent Clinical Event Committee, and the relevant provisions for evaluation are referred to in the Clinical Event Committee bylaws.

5 Statistical Considerations

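### Section 11 ties CEC adjudication to device- or procedure-associated events and admits only CEC determinations, which conflicts with the wider CEC remit elsewhere and with safety endpoints defined regardless of cause

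*Protocol*

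**What the plan says.** Section 11 (Clinical Event Committee) contains three statements:

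- It opens broadly: the CEC "will evaluate safety endpoints data and the sponsor will appoint a CEC".
- It then describes the committee's task as to "adjudicate all SAE and/or AEs associated with the observational device or observational procedure identified".
- It closes with an exclusive-source rule: "Only CEC's determinations of the collected data" "were used for the analysis of safety endpoints", apart from a parenthesis in between that lists the records the committee reviews.

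Other places describe the remit without a relatedness limit:

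- The synopsis heads the whole list of five safety endpoints, including all-cause mortality and AE/SAE, with "Safety Endpoints[Adjudicated by Clinical Event Committee (CEC".
- Section 4.6 says: "Evaluation and adjudication of safety endpoints as specified in the protocol will be completed by an independent Clinical Event Committee".
- Section 8.3 makes the CEC responsible for adjudicating the study's adverse events.
- Section 10.1.3 has the CEC determine severity and relatedness independently.
- Section 4.4.1 sends all strokes to the CEC and has it judge whether a death is neurogenic.

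The endpoint definitions carry no relatedness condition. Under the heading of all-cause mortality, section 4.4.1 states: "Mortality refers to the proportion of dead patients in the total number of patients". Section 10.1.1 defines an AE as any untoward medical occurrence, related to the device or not. AE/SAE is the fifth safety endpoint.

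**The concern.** Either rule in section 11 would do little harm alone. A committee that adjudicates only associated events is workable if the remaining events are counted from site records. An exclusive-source rule is workable if the committee sees every event. Together they mean that an event outside the adjudication clause has no determination and so no stated way into the analysis, and the protocol provides no fallback to the investigator's record.

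At stake are cause-independent safety rates in a study that section 2.1.3 says is run to meet NMPA requirements for long-term safety information, with an analysis completed each year (section 5.4). A relatedness screen on such endpoints can only lower them. It would also give the reported figure a different meaning: an AE rate would in part be a rate of related AEs.

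**Working it through.** The protocol states no sample size, event count or relatedness share, so there is no figure to reproduce. The check compares the texts.

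**Step 1. Two ways to read the adjudication clause in section 11.**

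- Reading A: all SAEs, plus those AEs that are associated with the device or procedure.
- Reading B: the words on association govern both nouns, so only associated SAEs and associated AEs are adjudicated.

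**Step 2. Apply the exclusive-source rule to each class of event.**

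- Strokes: they reach the CEC on either reading, because section 4.4.1 says so expressly.
- Deaths: on reading A they reach the CEC, because section 10.2.1 makes an AE that causes death an SAE. On reading B, section 11 alone would not send an unrelated death to the CEC. Section 4.4.1 nevertheless has the CEC decide whether a death is neurogenic, which presupposes that it sees deaths of any cause.
- Other unrelated SAEs: covered on reading A. Not covered by the section 11 clause on reading B, but covered by the synopsis and sections 4.6 and 8.3.
- Unrelated non-serious AEs: outside the section 11 clause on both readings. They are covered only if the wider wording in the synopsis and sections 4.6 and 8.3 overrides it, and the protocol does not say which governs.

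**Step 3. Who decides what counts as associated?** Section 10.1.3 gives relatedness to the CEC. Sections 10.1.4 and 10.2.2 have the investigator rate causality as well. If the CEC's rating defines the set, the clause is circular, because the committee must see an event to decide whether it belongs before the committee. If the investigator's rating defines it, a site judgement selects what the committee receives. The protocol does not say which is meant.

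**Step 4. Direction and size.** For event counts within an affected class:

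reported rate = true rate × share of events classed as associated.

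The share lies between 0 and 1, so the rate is unchanged if every event is classed as associated and otherwise falls. For the proportion of patients with any AE on reading A, the patients lost are those whose only AEs are non-serious and unrelated. That group may be anything from nobody to all patients who have only such AEs. The documents give none of these quantities, so no numerical understatement can be stated.

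**The case against.** The strongest reply is that one loosely worded clause should not be taken as the whole remit. The synopsis, sections 4.6 and 8.3 and the opening of section 11 all describe a committee that adjudicates the safety endpoints or the study's adverse events without limit. Section 10.1.3 has it determine relatedness, which requires it to see events before they are classified. The exclusive-source sentence might be meant as a precedence rule for cases where site and committee disagree. Operational scope is left to CEC bylaws or a charter, which are not at hand.

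Much of this stands, and it rules out several stronger conclusions that a reader might draw from section 11:

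- That the plan drops unrelated deaths from all-cause mortality. This needs reading B and must set aside the synopsis, the mortality definition and the neurogenic-death provision.
- That only strokes are protected. The synopsis marks all five safety endpoints as adjudicated.
- That the CEC never sees unrelated events. Section 10.1.3 points the other way, and nothing says that the site's causality rating controls referral.
- That section 4.4.1 (5) is a site filter because the principal investigator "shall assess whether an AE/ SAE meet the definition of surgical complication and safety collection index". The same section has all AEs recorded. This step decides only whether a further form page is completed, and it does not say that other events are withheld.

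What the reply does not do is reconcile the text. The wider statements show that the protocol gives the committee at least two remits, and the narrower one sits in the only section that carries the exclusive-source rule. Reading that rule as mere precedence is possible, but it is not what the sentence says. A charter could settle practice but would not remove the contradiction from the protocol.

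**Conclusion.** The protocol contradicts itself on which events the CEC adjudicates, and the contradiction matters because section 11 lets only CEC determinations into the safety analysis. The clear exposure is unrelated non-serious AEs: followed literally, section 11 keeps them out of an AE endpoint that is defined regardless of relatedness. Exposure of unrelated SAEs and deaths is conditional on reading B, which the rest of the protocol argues against. Strokes are not exposed.

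The documents do not establish that mortality or SAE rates will be understated, and the amount by which the AE rate might be understated is unknown. The conclusion rests on the literal wording of section 11 and on the absence of any stated fallback to site records. It is a wording fault that should be corrected, not a demonstrated bias.

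**What to change.** Reword section 11 to agree with the synopsis and sections 4.6, 8.3 and 10.1.3:

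- All deaths, strokes, SAEs and candidate lesion-related events go to the CEC, whatever relatedness the site has assigned.
- All-cause mortality is counted from every recorded death. The CEC classifies cause and relatedness but does not decide whether a death counts.
- AEs that the CEC has not adjudicated are counted from the investigator's record. Where a CEC classification exists, it takes precedence.
- The exclusive-source sentence is restated as that precedence rule.

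The CEC charter should carry the same scope. The cost is protocol and charter wording, with ethics committee approval of the amendment as section 12 requires, and possibly a few more cases for a committee that is already planned. No extra AE recording is needed, because section 10.1.4 already requires all AEs to be recorded.

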16.1 Responsibilities of Sponsor

- (1) The sponsor of a medical device clinical study shall establish a quality management system covering the entire process of the clinical study to ensure that the study complies with relevant laws and regulations, and to protect the rights and safety of patients.
- (2) Prior to the start of the medical device clinical study, the sponsor shall submit the required documents to the EC through the Principal Investigator.
- (3) The sponsor is responsible for the authenticity and compliance of the medical device clinical study. If the sponsor is a foreign entity, it must designate a domestic legal entity in China as its agent in accordance with relevant laws and regulations, and the agent shall assist the sponsor in fulfilling its responsibilities.
- (4) The sponsor shall sign contracts with the medical device clinical research institution and the principal investigator, clearly defining the rights and obligations of all parties involved in the clinical study.
- (5) Before the start of the medical device clinical study, the sponsor is responsible for organizing training related to the study, such as on the clinical study protocol, SOPs, and other relevant documents.
- (6) To ensure the quality of the clinical study, the sponsor may organize audits conducted by auditors who are independent of the clinical study and have the necessary training and experience, to assess whether the study is being conducted in accordance with the study protocol and relevant laws and regulations.

- (7) The sponsor shall ensure that the clinical study is conducted in compliance with the clinical study protocol. If the sponsor discovers that the clinical research institution or investigator is not adhering to the protocol or relevant laws and regulations, it must promptly identify the issue and correct it. If the non-compliance is serious or persists, the sponsor shall terminate the participation of the institution and investigator in the study.
- (8) The sponsor shall have the necessary facilities and conditions for storing essential clinical study documents and shall establish a document management system. The essential documents of the medical device clinical study shall be divided into three parts based on the study phase: preparatory phase documents, in-progress phase documents, and post-completion or termination documents.
- (9) The sponsor and the medical device clinical research institution shall ensure the integrity of essential clinical study documents during the storage period, preventing intentional or unintentional alterations or loss. The sponsor shall retain the essential documents until the medical device is no longer in use.

16.2 Responsibilities of Medical Device Clinical Research Institutions

- (1) The medical device clinical research institution shall establish a quality management system that covers the entire process of conducting the clinical study, to ensure that the principal investigator fulfills their research-related responsibilities, provides proper medical care to patients, and ensures the authenticity of the data generated from the study.
- (2) Before accepting a medical device clinical study, the clinical research institution shall assess relevant resources based on the characteristics of the observational device, ensuring that it has the appropriate qualifications, personnel, facilities, and conditions.
- (3) The medical device clinical research institution and investigators shall cooperate with monitoring and auditing organized by the sponsor, as well as inspections conducted by drug regulatory and health administration departments.
- (4) The medical device clinical research institution shall properly maintain clinical study records and essential documents in accordance with relevant laws and regulations, as well as the contract with the sponsor.
- (5) The medical device clinical research institution shall have the necessary facilities and conditions for storing essential documents and shall establish a management system for these documents. The essential documents shall be divided into three parts based on the study phase: preparatory phase documents, in-progress phase documents, and post-completion or termination documents.

(6) The medical device clinical research institution shall ensure the integrity of essential documents during the storage period, preventing intentional or unintentional alterations or loss.

